7.2.8 Biomarker Evaluable Set

The biomarker evaluable set will consist of all patients who receive at least one dose of study drug and have at least one of ICOS, FOXP3 and CD8 cells results available for analysis within the relevant phase. This population will be used for the analyses of ICOS, FOXP3 and CD8 cells biomarkers.

8.0 Conventions and Derivations

8.1 Baseline Values

Baseline is defined as the last measurement prior to first study drug administration.

8.2 Change from Baseline

Change from baseline (CFB) will be calculated as (post-baseline value – baseline value). Change from baseline will be calculated for patient who have both a baseline and post-baseline value as applicable.

8.3 Prior and Concomitant Medication

Medications administered to patients during the study are captured on a log CRF page. Medications are considered prior medications if they have a start date prior to the date of first dose of study medication or a partial start date which indicates the medication was begun prior to the first dose of study treatment.

Concomitant medications are defined as medications administered to patients on or after the first dose of study medication and before the last dose of study medication.

The medication taken after the last dose of study medication will be considered as post-study and will be included in subject data listings.

The medication with start date prior to first dose of study medication and ongoing in the study will be included in subject data listing and will be flagged as prior and concomitant.

Collected prior and concomitant medications will be coded using the World Health Organization (WHO) medical dictionary.

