# 5.6.2 Follow-up for Toxicities

- The emergence of irAEs may be anticipated based on overall experience in clinical studies with similar immunomodulators.
- An irAE is a clinically important AE of unknown etiology associated with the study • drug exposure. IrAEs are typically low grade and self-limited, often occurring after multiple doses, and most frequently involving the GI tract (diarrhea/colitis), skin (rashes), liver (hepatitis), and endocrine systems (a variety of endocrinopathies) and lung (pneumonitis). Serologic, histologic (tumor sample) and immunological assessments should be performed as deemed appropriate by the Investigator, to verify the immune related nature of the AE, and exclude the neoplastic, infectious or metabolic origin of the AE. Management Algorithms (Table 5-5) have been developed to assist Investigators in assessing and managing the following groups of Aes: Infusion reactions, Hematological, Cardiological, GI, Renal, Pulmonary, Hepatic, Endocrinopathy, Dermatological, Neurological, Ophthalmological, and Rheumatological Aes.
- Patients whose treatment is interrupted or permanently discontinued due to an irAE, AE or clinically significant laboratory value, must be followed-up at least once a week (or more frequently if required by institutional practices, or if clinically indicated) for 4 weeks, and subsequently at approximately 4-week intervals, until resolution or stabilization of the event, whichever comes first. Appropriate clinical experts should be consulted as deemed necessary.
- In case of a suspected irAE, the relevant immunological assessments (eg, rheumatoid factor, anti-deoxyribonucleic acid (DNA) Ab, etc.) should be performed and guidelines as outlined in Table 5-5 (and laboratory assessments Section 6.5.6) should be followed.

All patients must be followed up for irAEs, Aes and SAEs for 90 days following the last dose of KY1044 as single agent or in combination with atezolizumab.

Table 5-5 outlines the follow-up evaluation recommended for selected toxicities. For any irAEs/Aes Grade 1 and/or Grade 2, treatment with KY1044 and atezolizumab (if applicable) should be maintained at the determined dose and schedule, unless otherwise specified in Table 5-5.

10-Nov-2021 Version number: 1

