8.8.2 Treatment Emergent Adverse Events

A treatment emergent adverse event (TEAE) is defined as an AE observed after starting administration of the specific treatment. If a patient experiences an event both prior to and after starting administration of a treatment, the event will be considered a TEAE (of the treatment) only if it has worsened in severity (i.e., it is reported with a new start date) after starting administration of the specific treatment, and prior to the start of another treatment (if any) or up to 21 days after the last dose.

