10.3.2 Concomitant Medications

The medications received concomitantly with study drug, categorized by medication group and subgroup according to WHO Drug Enhanced [Version March 2016], will be summarized. The number and percentage of patients using each medication will be displayed together with the number and percentage of patients using at least one medication with each anatomical therapeutic chemical (ATC) and preferred term (PT).

Prior, concomitant and post study medications will be listed.

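### The SAP closes the concomitant-medication window before the last dose, so its table omits drugs first started from that day on

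*SAP*

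**What the plan says.** SAP section 8.3 sorts medications by the first and last dose of study medication. Concomitant medications are those "medications administered to patients on or after the first dose of study medication and before the last dose of study medication". For what comes afterwards: "The medication taken after the last dose of study medication will be considered as post-study and will be included in subject data listings". For a drug begun before treatment and still running, "The medication with start date prior to first dose of study medication and ongoing in the study will be included in subject data listing", with a flag as both prior and concomitant.

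SAP section 10.3.2 summarises "The medications received concomitantly with study drug, categorized by medication group and subgroup", giving the number and percentage of patients using each. It then adds: "Prior, concomitant and post study medications will be listed". No other planned output tabulates drugs classed as post-study.

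Other sections look past the last dose. SAP 8.7.1 adds 21 days to the last dose date when it computes treatment duration; in combination patients it also computes a joint duration that runs to the later of the two drugs' last doses. SAP 8.8.2 on treatment-emergent adverse events includes the phrase "up to 21 days after the last dose". Protocol section 5.6.2 says: "All patients must be followed up for irAEs, Aes and SAEs for 90 days following the last dose". Protocol Tables 6-1 and 6-2 schedule a review of concomitant medications at the end-of-treatment visit and at the 90-day safety visit.

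**The concern.** When a toxicity stops treatment for good, no dose follows it. A steroid or other immunosuppressant newly started for that toxicity therefore comes on or after the last dose, outside the window in SAP 8.3. Protocol Table 5-5 pairs permanent discontinuation with corticosteroids for several toxicities, among them Grade 3 and 4 hepatitis and Grade 3 and 4 encephalopathy. Under protocol section 5.2.4, an infusion reaction above Grade 2 also ends treatment. If that happens at the only infusion, the first and last dose coincide and nothing started afterwards can be concomitant.

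At stake is how the concomitant-medication table reads. In a first-in-human immunotherapy study reported by dose level, a reader may use it to see how often immunosuppression was needed. As defined, it can miss patients whose first use came with the event that stopped treatment. If dose levels differ in how early patients stop, comparing them on this table could mislead.

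**Working it through.** The plan states no figure to reproduce. The check applies the definitions in SAP 8.3 by calendar date to every day on which a drug could be started.

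**Inputs**
- Window: first dose included, last dose excluded (SAP 8.3).
- Treatment period: first dose to last dose + 21 days, both ends counted (SAP 8.7.1).
- Dosing interval: 21 days (protocol section 5.3), assumed exact, with no delayed or skipped doses.

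**Formulas.** Let day 0 be the first dose and n the number of doses.
- Last-dose day: L = 21(n − 1).
- Start days in the treatment period, 0 to L + 21: L + 22 = 21n + 1.
- Start days that count as concomitant, 0 to L − 1: L = 21(n − 1).
- Start days after the last dose, L + 1 to L + 21: always 21, and listed only.
- Last-dose day itself: 1, neither before nor after the last dose.
- Check: 21(n − 1) + 1 + 21 = 21n + 1.

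| Doses | Last-dose day | Days in period | Concomitant | Share | Listed only | In no category |
|---|---|---|---|---|---|---|
| 1 | 0 | 22 | 0 | 0% | 21 | 1 |
| 2 | 21 | 43 | 21 | 49% | 21 | 1 |
| 3 | 42 | 64 | 42 | 66% | 21 | 1 |
| 6 | 105 | 127 | 105 | 83% | 21 | 1 |

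With a window running to last dose + 21 days inclusive, the counts become 22/22, 43/43, 64/64 and 127/127.

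**Worked case.** After four doses the last dose is on day 63. A steroid started on day 73, ten days later, is post-study and untabulated, although day 73 lies inside the treatment duration of SAP 8.7.1, which runs to day 84.

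**Limits of the literal reading**
- Drugs are sorted by start date. A drug started on the last-dose day and continued could also be read as taken after the last dose, hence post-study. Either way it is not tabulated.
- With clock times instead of dates, a drug given shortly before the last infusion on the same day would count.
- Protocol section 5.2.4 allows atezolizumab to be delayed to the next day after a reaction to KY1044. A one-cycle combination patient treated that way has a one-day window. The empty window is strict for a single infusion.
- Drugs begun before the first dose and ongoing carry the prior-and-concomitant flag. The problem concerns drugs started on treatment.

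**The case against.** The strongest reply is that this is a descriptive table supporting no endpoint. The Phase 1 primary endpoints are adverse events, tolerability and DLTs; the Phase 2 primary endpoint is ORR. Protocol section 9 promises no concomitant-medication analysis. The severe events are tabulated in SAP 10.7.1 and 10.7.2, by grade, seriousness and drug discontinuation. The medications are collected through day 90 and listed. All of this stands, and it limits the weight of the point. It does not make the window correct.

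A reader might infer more than the documents support, in three ways.

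- *That all immunosuppression for treatment-ending toxicity is lost.* Table 5-5 also describes courses in which steroids come before the last dose. Grade 2 colitis may be treated, dosing resumed, and treatment stopped for good on a recurrence at Grade 3 or above. Inflammatory arthritis may be given prednisone at Grade 1 while treatment continues. Such use is tabulated. Under protocol section 8, a patient who stops atezolizumab for an acute infusion reaction may continue KY1044, which moves the last dose later. The complete loss applies only to drugs first started on or after the last dose.
- *That the uncovered share of treatment time, roughly 1/n, is the size of the under-reporting.* It is a share of calendar days under exact spacing. The table counts patients, and a patient is missed for a given drug only if its first use falls on or after the last dose. The documents give no rate for that.
- *That the adverse event is cleanly on-treatment while its rescue drug is not.* In SAP 8.8.2 the 21-day phrase sits in the sentence on worsening of earlier events: "prior to the start of another treatment (if any) or up to 21 days after the last dose". SAP 8.8.3 labels events starting in those same 21 days as post-treatment. The two sections conflict, so the firmer reference is the treatment duration in 8.7.1.

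**Conclusion.** The point holds as a fault in a stated definition, of minor to moderate weight. On its literal text, SAP 8.3 gives a single-infusion patient no concomitant window, leaves a drug started on the last-dose day uncategorised, and sends every drug first started afterwards to listings only. The table will understate medication use around treatment-ending toxicity. The direction is clear for drugs newly started then; the number of patients affected cannot be estimated from the documents. No data are lost, and the ORR, DLT and adverse event analyses do not change. The conclusion rests on the date-based reading of 8.3 and on the absence of any other planned table for post-study drugs.

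**What to change.** In SAP 8.3, define concomitant medication as any drug taken on or after the first dose and up to and including 21 days after the last dose of any study drug, in line with the treatment duration in 8.7.1. Class drugs started later as post-treatment rather than post-study, since patients are still in safety follow-up. In the same revision, reconcile the 21-day wording of 8.8.2 and 8.8.3, so that one period does not carry two labels.

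A separate summary of immunosuppressants given for adverse events up to day 90 would be informative but is optional; neither document promises it.

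The cost is SAP wording and one programming flag. No new data are needed, because medications are already reviewed at end of treatment and at day 90. The change should be made before database lock, when SAP section 4.0 has the final version approved.

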8.4 End of Study for Individual Patient

The end of study for each patient will be either:

- At the end of the 90 day safety follow-up period after stopping treatment, for the last patient in the study.
- At the overall end of the study for all patients, who are still in follow-up for PFS and or survival as determined by the Sponsor.

The end of the study recorded in the CRF will be used to count patients who complete the overall study.

8.5 Time since Initial Diagnosis

The time since initial diagnosis in years will be derived as (date of informed consent – date of initial diagnosis)/365.25. In case of missing or partial date of diagnosis the time since initial diagnosis will be missing.

8.6 Efficacy Analysis

8.6.1 Best Overall Response

The BOR for each patient is defined as the best response per RECIST 1.1 or iRECIST among all responses recorded from start of treatment until progressive disease, initiation of new anti-cancer therapy, death, or analysis cut-off date, whichever comes first, with a response of CR or iCR, PR or iPR, SD or iSD, progressive disease or immune-unconfirmed progressive disease (iUPD) or immune-confirmed progressive disease (iCPD) and then not evaluable (NE).

For confirmed responses, an equal or superior response must be observed at a subsequent time point at least 4 weeks after the initial assessment. In the case of SD, measurements must have met the SD criteria

at least once no less than 7 weeks after first study drug administration, regardless of whether the endpoint is confirmed or unconfirmed responses.

8.6.2 Objective Response Rate

Patients' tumor imaging results will be assessed by the Investigator in screening and periodically after start of treatment in each study phase for response per RECIST 1.1 and iRECIST. Response categories by RECIST as indicated by Investigator will be CR, PR, SD, PD, or NE and by iRECIST will be iCR, iPR, iSD, iUPD, iCPD, or NE.

ORR accordingly to RECIST 1.1 is defined as the proportion of patients with a measurable disease at baseline and with BOR of CR or PR. The response of CR or PR must be confirmed by a later scan conducted at least 4 weeks after the initial response is observed. In case of SD, measurements must have met the SD criteria at least once no less than 7 weeks after first study treatment administration.

The ORR for iRECIST is defined as the proportion of patients with a measurable disease at baseline and having achieved complete immune-response (iCR) or partial immune-response (iPR) by iRECIST.

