# 4.2 Inclusion Criteria

Patients eligible for inclusion in this study must meet all of the following criteria:

- 1. Written informed consent must be obtained prior to any procedures
- 2. Age  $\geq 18$  years ( $\geq 20$  years in Taiwan)
- 3. Histologically documented advanced/metastatic malignancies
- 4. Phase 1 and Phase 2 patients with advanced/metastatic malignancies who have measurable disease (non-measurable disease is allowed only in Phase 1) as determined by RECIST 1.1 (refer to Appendix 1) will be eligible if, according to the NCCN guidelines, there are no available therapies known to confer a clinical benefit for their disease, or they have exhausted all such available options. Additionally, the following specific tumor indications will be enrolled:

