Definitions of measurable and non- measurable disease; numbers and site of target disease	Measurable lesions are $\geq 10$ mm in diameter ( $\geq 15$ mm for nodal lesions); maximum of five lesions (two per organ); all other disease is considered non-target (mast be $\geq 10$ mm in short axis for nodal disease)	No change from RECIST 1.1; however, new lesions are assessed as per RECIST 1.1 but are recorded separately on the case report form (but not included in the sum of lesions for target lesions identified at baseline)
Complete response, partial response, or stable disease	Cannot have met criteria for progression before complete response, partial response, or stable disease	Can have had iUPD (one or more instances), but not iCPD, before iCR, iPR, or iSD
Confirmation of complete response or partial response	Only required for non-randomised trials	As per RECIST 1.1
Confirmation of stable disease	Not required	As per RECIST 1.1
New lesions	Result in progression; recorded but not measured	Results in iUPD but iCPD is only assigned on the basis of this category if at next assessment additional new lesions appear or an increase in size of new lesions is seen (25 mm for sum of new lesion target or any increase in new lesion non-target), the appearance of new lesions when none have previously been recorded, can also confirm iCPD
Independent blinded review and central collection of scans	Recommended in some circumstances —eg. in some trials with progression- based endpoints planned for marketing approval	Collection of scans (but not independent review) recommended for all trials
Confirmation of progression	Not required (unless equivocal)	Required
Consideration of clinical status	Not included in assessment	Clinical stability is considered when deciding whether treatment is continued after iUPD

Table 1

"i" indicates immune responses assigned using iRECIST. RECIST=Response Evaluation Criteria in Solid Turnours. iUPD=unconfirmed progression. iCPD=confirmed progression. iCR=complete response. iPR=partial response. iSD=stable disease.

Lancet Oncol. Author manuscript: available in PMC 2017 October 19.

Seymour et al.

Page 21

Table 2

Assignment of timepoint response using iRECIST

-
D.
-
-
-
2
0
-
-
<
-
m
-
~
10
90
0
-
4

Author Manuscript

d	Timepoint response with no previous IUPD in any category	This point response with previous iUPD in any category $\ensuremath{^\circ}$
Target lesions: i CR; non-target lesions: iCR; new lesions: no	iCR	iCR

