10.5.2.2 Primary Analysis

The primary endpoints in Phase 1 are safety endpoints (see SAP Section 12.3 and 12.7).

The number and percentage of patients with confirmed CR or PR per RECIST 1.1 will be presented for all patients in FAS. The ORR will be accompanied by the 2-sided exact 95% Clopper-Pearson CI.

The waterfall plots of best percent change from baseline and maximum tumor size reduction from baseline as assessed by the investigator according to RECIST 1.1 will be provided for the FAS population.

The spider plot for percent change from baseline in tumor size will be provided for the FAS population.

Lesions assessed by the investigator (target, non-target, and new lesions) and investigator-reported overall tumor response assessment as per RECIST 1.1 will be presented in listings.

The subject-data listing will be provided for tumor assessment and tumor response.

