10.5.3.4 Objective Response Rate

ORR per iRECIST for both the study phases and ORR per RECIST 1.1 for Phase 1 patients in FAS will be summarized with the same approach described in SAP section 12.5.2.2.

The subject-data listing will be provided for tumor assessment and tumor response.

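### SAP 8.6.2 conflicts with SAP 10.5.2.2 and 10.5.3.4 on the Phase 1 ORR denominator and on whether iRECIST responses must be confirmed

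*SAP*

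**What the plan says.** **Who counts, and out of whom.** SAP 8.6.2 defines the endpoint: "ORR accordingly to RECIST 1.1 is defined as the proportion of patients with a measurable disease at baseline and with BOR of CR or PR". Its iRECIST counterpart carries the same measurable-disease condition. Neither definition names a denominator. The analysis text in SAP 10.5.2.2 does: "The number and percentage of patients with confirmed CR or PR per RECIST 1.1 will be presented for all patients in FAS". SAP 10.5.3.4 extends this to the secondary endpoints, namely iRECIST ORR in both phases and, for RECIST 1.1, "ORR per RECIST 1.1 for Phase 1 patients in FAS will be summarized with the same approach". The FAS (SAP 7.2.3) is everyone allocated to study drug, with no measurable-disease condition. Protocol 4.2 requires measurable disease at entry except that "non-measurable disease is allowed only in Phase 1".

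**Confirmation.** For RECIST 1.1, SAP 8.6.2 adds: "The response of CR or PR must be confirmed by a later scan conducted at least 4 weeks after the initial response is observed". The iRECIST paragraph that follows has no such sentence and asks only for patients "having achieved complete immune-response (iCR) or partial immune-response (iPR) by iRECIST". SAP 8.6.1 gives one best-overall-response definition for both criteria. Its 4-week rule is conditional: it applies where responses are confirmed, and the text allows for unconfirmed endpoints without saying which they are. SAP 10.5.3.4 sends the iRECIST ORR to section 12.5.2.2, a number from the old layout. The intended target, 10.5.2.2, speaks of confirmed CR or PR under RECIST 1.1 only. Protocol 6.2.1.1 requires confirmation of response under RECIST 1.1; Protocol 6.2.1.2 (iRECIST) deals only with confirming progression. In the guideline reprinted as Protocol Appendix 2, the table comparing the two criteria says of confirming complete or partial response: "Only required for non-randomised trials", and gives the iRECIST rule as identical. SAP 6.3 states that the study has no randomisation.

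**The concern.** A programmer needs one numerator, one denominator and one confirmation rule for each ORR. Here the definition and the analysis text do not give the same answer.

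In Phase 1, where ORR is a named secondary endpoint, the same data can yield different percentages depending on which section is followed. For iRECIST, the definition taken alone counts a single unconfirmed iCR or iPR. That ORR would then sit beside a confirmed RECIST 1.1 ORR, and the two would differ for a reason unrelated to the criteria. What is at stake is the interpretability of reported secondary endpoints, and discretion left to the analyst once the data are known.

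**Working it through.** **The plan's own figures.** SAP 6.2 illustrates ORR with two-sided 80% intervals. Exact Clopper-Pearson limits reproduce them: 3/15 gives 7.6% to 39.3% (stated 8%, 39%), and 8/40 gives 12.0% to 30.5% (stated 12%, 30%). The other four also match after rounding. None depends on measurable disease or confirmation, so they neither expose nor settle the conflict. The 20% base rate used below comes from these examples.

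**Part 1: Phase 1 denominator.** Three readings are possible:

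- (a) 8.6.2 for the numerator and 10.5.2.2 for the denominator: measurable responders over all FAS.
- (b) 8.6.2 read as restricting the population: measurable responders over measurable patients.
- (c) 10.5.2.2 alone: any confirmed CR or PR over all FAS.

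In the reprinted RECIST 1.1 (Protocol Appendix 1), patients with only non-target disease can be CR, non-CR/non-PD, PD or not evaluable, but never PR. Readings (a) and (c) therefore differ only if such a patient has a confirmed CR. Readings (a) and (b) differ by the factor (1 − m), where m is the share of Phase 1 patients with only non-measurable disease. The documents do not give m; 10% to 30% is assumed.

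With about 150 Phase 1 patients (SAP 6.2) and 20% ORR among measurable patients:

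| m | Measurable n | Responders | Reading (b) | Reading (a) |
|---|---|---|---|---|
| 10% | 135 | 27 | 27/135 = 20% | 27/150 = 18% |
| 20% | 120 | 24 | 24/120 = 20% | 24/150 = 16% |
| 30% | 105 | 21 | 21/105 = 20% | 21/150 = 14% |

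In one escalation component at its maximum of 36 with m = 30% (25 measurable after rounding, 5 responders), the reported result is 5/25 = 20.0% (exact 95% CI 6.8% to 40.7%) or 5/36 = 13.9% (4.7% to 29.5%).

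In Phase 2, eligibility makes m = 0, so the readings coincide apart from any patient entered in error.

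**Part 2: iRECIST confirmation.** Let u be the share of first responses not confirmed. The documents do not give u; 10% to 25% is assumed. Confirmed ORR = first responses × (1 − u) / n. With 8/40 first responses:

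- u = 10%: 8 × 0.90 / 40 = 7.2/40 = 18% (7.2 is an expected count).
- u = 25%: 8 × 0.75 / 40 = 6/40 = 15%.
- Counted without confirmation: 8/40 = 20%.

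The gap is 2 to 5 percentage points. If 10.5.3.4 is followed as presumably intended, it is zero.

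**The case against.** The strongest reply has four parts.

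1. A reader might infer that Phase 1 ORR is biased downward. The documents do not support that. The reprinted RECIST 1.1, where response is secondary and not all patients have measurable disease, accepts either all patients or the measurable subset, provided the choice is stated in advance (its text appears under Phase III trials). The 18% to 14% figures are the gap between two acceptable denominators, not an error in one of them. This stands. What remains is that the choice has not been made.

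2. A reader might infer that the SAP abandons confirmation for iRECIST. That also goes too far. SAP 8.6.1 covers both criteria, 10.5.3.4 points to a confirmed-response analysis, and the adopted guideline keeps confirmation here. None of these closes the gap, though: 8.6.1 is conditional, the cross-reference is stale and its target names only RECIST 1.1 responses, and the definition itself is silent directly after requiring confirmation for RECIST 1.1.

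3. It is tempting to say that Phase 2 decisions are at risk. Protocol 3.1.4 opens the single-agent part on activity in at least one patient, and the combination part in chosen indications or any indication showing activity. These are signals, not an ORR percentage, so the denominator does not enter.

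4. An iRECIST ORR above the RECIST 1.1 ORR is not itself a fault, since iRECIST allows a response after unconfirmed progression. The SAP plans no formal comparison of the two. This stands. Unequal confirmation would simply add a second, avoidable source of difference that readers could not separate from the first.

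**Conclusion.** The point holds as two internal conflicts in the SAP, not as a demonstrated bias in either direction.

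For Phase 1, a 20% ORR among measurable patients would be reported as 20%, or as 18%, 16% or 14% if 10%, 20% or 30% of patients have only non-measurable disease. For iRECIST in either phase, following 8.6.2 alone would put the rate about 2 to 5 points above its confirmed value at 8/40 first responses, if 10% to 25% go unconfirmed. This comes on top of any excess that iRECIST permits by design. Both sets of shares are assumptions, and the gaps lie well inside the sampling uncertainty of such small groups. The conclusion that the sections disagree does not depend on them.

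The Phase 2 primary endpoint is essentially unaffected: it requires measurable disease at entry and already has an explicit confirmation rule. The matter should be settled before database lock because it concerns reported secondary endpoints and is cheap to correct.

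**What to change.** In SAP 8.6.2 and 10.5.3.4:

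- State that Phase 1 ORR, under both RECIST 1.1 and iRECIST, uses FAS patients with measurable disease at baseline as the denominator. Count not-evaluable patients as non-responders and give the all-FAS rate as supportive.
- State that the denominator in Phase 2 remains the FAS. The measurable subset should not replace it there: the FAS is the primary efficacy population, and Protocol 8 foresees patients started on treatment in error, so the two sets need not be identical.
- Add to the iRECIST ORR definition that an iCR or iPR counts only if a repeat scan, no earlier than 4 weeks after it was first documented, confirms it. Show unconfirmed iRECIST responses on a separate, labelled line if they are wanted.
- Replace the reference to 12.5.2.2 with 10.5.2.2, and make clear that for iRECIST the approach applies to confirmed iCR and iPR.

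The cost is a few sentences, one supportive Phase 1 row and no new data. The iRECIST ORR may come out slightly lower.
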